2.5.8 Sample Size

In order to identify significant differences in slopes of predictor of response magnitude vs pain reduction curve in lidocaine group and placebo group, 34 patients will be required for this cross-over trial. The calculation is based on the ability to detect difference of 14 (SD 18.21) units between correlation coefficients of the two curves, based on our pilot data [14] (the calculation was performed for 85% power, and $\alpha = 0.025$, after Bonferroni correction for two comparisons; MPT and HPT). The enrollment will continue until 35 participants have completed both phases of treatment.

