1. SYNOPSIS

Study Title	Predicting individual response to analgesic treatment with lidocaine in painful diabetic peripheral neuropathy (DPN)
Objective	To test, in a prospective, randomized, double-blind, placebo-controlled study, whether quantitative sensory measures predict the response to treatment with systemic sodium channel blocker lidocaine in patients with painful DPN.
Hypothesis	Among patients with painful DPN, those with higher mechanical pain threshold (MPT) or heat pain threshold (HPT) are more likely to respond to analgesic treatment with intravenous lidocaine.
Study Period	Planned enrollment duration: Approximately 24 months Planned study duration: 3 days per subject (1 enrollment and 2 treatment visits), with 3 week washout between the last 2 visits.
Number of Patients	35 evaluable patients with painful DPN completing the study
Study Treatment	Single intravenous 40-min infusion with 5mg/kg lidocaine or normal saline (placebo).
Study Design	Prospective, randomized, double-blind, placebo-controlled, cross-over study.
Inclusion and Exclusion Criteria	
Inclusion criteria:
 
 1. Age ≥ 18; 2. Diagnosis of Diabetes Mellitus (Fasting Plasma Glucose > 126 mg/dL and/or HbA1C $> 6.5\%$); 3. Distal symmetric pain in lower extremities with duration of more than 3 months; 4. Presence of either numbness or at least 1 sensory disturbance (increased or decreased sensitivity) in the feet. 5. Spontaneous pain with intensity of ≥ 4 on 0-10 Numerical Rating Scale (NRS). 
Exclusion criteria:
 
 1. Not giving consent to participate in the study; 2. Unable to complete self-report pain questionnaire; 3. History of moderate to severe renal or liver failure; 4. History of other central or peripheral neurologic disorders; 5. History of cardiac arrhythmias; 6. Contraindication to intravenous lidocaine; 7. Pregnancy or lactation.
Measurements	
Baseline sensory testing:
 
 1. Quantitative sensory testing (QST): Thermal detection and pain thresholds, mechanical detection and pain thresholds, pressure pain thresholds, temporal summation presence, and conditioned pain modulation (CPM). 2. Spontaneous pain at baseline on 0-10 Numerical Rating Scale (NRS); 3. Assessment of pain symptoms on Neuropathic Pain Symptom Inventory (NPSI) and Brief Pain Inventory (BPI).

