2.3 Objective

The objective of the proposed study is to test whether quantitative sensory measures predict the response to treatment with systemic sodium channel blocker lidocaine in patients with painful DPN.

The specific aims of this study are:

1. To investigate whether the baseline mechanical pain threshold (MPT) predicts the individual response to intravenous lidocaine treatment in DPN.
2. To investigate whether the baseline heat pain threshold (HPT) predicts the individual response to intravenous lidocaine treatment in DPN.

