2.5.7 Statistical Methods

The comparison between the analgesic effectiveness associated with each putative predictor of response (MPT and HPT) to lidocaine and to placebo will be performed by the following method: We will perform t-test in a multiple linear regression model to test the difference between slopes of predictor magnitude vs. response magnitude, namely: 1) Compare the slopes of MPT magnitude vs. lidocaine response magnitude (% reduction in pain intensity) curve, and MPT magnitude vs. placebo response magnitude (% reduction in pain intensity) curve. The same procedure will be performed for HPT predictor.

The time point for primary effectiveness (pain reduction) outcome is 50 min after beginning of the infusion, based on our preliminary data. This will be calculated from the average of pain intensities at 40, 50 and 60 min from the beginning of the infusion.

The time point for secondary outcome of change in NPSI pain descriptors is 45 min after beginning of the infusion.

In exploratory phase, multiple regression analysis will be performed to investigate how the combination of various sensory phenotypes assessed in this study (i.e. MPT, HPT, WDT, MDT, CDT, CPT, and CPM) and lidocaine pharmacokinetics (area under the concentration-time curve, (AUC) and maximal plasma concentration (Cmax)) correlate with treatment response to lidocaine.

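### The plan's only multiplicity rule is Bonferroni at 0.025, stated in the sample-size text; Holm would give more power to confirm both predictors within the same implied 5% familywise limit

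*Combined protocol and SAP*

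**What the plan says.** Section 2.3 lists the two predictors as separate specific aims. The second is "To investigate whether the baseline heat pain threshold (HPT) predicts the individual response to intravenous lidocaine treatment in DPN". The Synopsis hypothesis is looser: "those with higher mechanical pain threshold (MPT) or heat pain threshold (HPT) are more likely to respond", which either predictor can satisfy.

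Section 2.5.7 describes the primary test: "We will perform t-test in a multiple linear regression model to test the difference between slopes". It compares the lidocaine and placebo slopes for MPT, and then "The same procedure will be performed for HPT predictor". It names no significance level, sidedness or multiplicity procedure.

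Multiplicity appears only in the sample-size text (section 2.5.8, repeated under Sample size in section 2.5.1). The alpha there is 0.025, "after Bonferroni correction for two comparisons; MPT and HPT". The same sentence says "the calculation was performed for 85% power" and gives the target as the ability to "detect difference of 14 (SD 18.21) units between correlation coefficients of the two curves". The result is 34 patients, with enrolment continuing until 35 have completed both periods. No step-down or ordered procedure appears anywhere.

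**The concern.** If the 0.025 in the sample-size text is carried into the analysis, each predictor is judged against 0.025 whatever the other one shows. Holm compares the smaller p-value with 0.025 and, if that is significant, the larger with 0.05. It needs no ordering of the predictors, no assumption about their dependence and no further data. The dependence matters here because both tests use the same patients and the same pain outcome.

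What is at stake is the second aim, meaning whichever predictor has the larger p-value and not HPT as such. With one predictor significant at 0.025 and the other at a p-value between 0.025 and 0.05, Bonferroni declares the second negative and Holm declares it positive. Because section 2.5.7 is silent, the plan also leaves room to choose the rule after that p-value has been seen.

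**Working it through.** **Inputs.** From section 2.5.8: alpha 0.025 per test, 85% power, difference 14, SD 18.21, 34 patients. From sections 2.3 and 2.5.7: two tests. The familywise level is implied: 2 x 0.025 = 0.05. Not given, and therefore assumed: sidedness, whether 18.21 is a per-period SD or the SD of the paired difference, and the correlation rho between the two test statistics (taken as 0 to 0.8).

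**The plan's own figure.** Treat 18.21 as a per-period SD with no within-patient correlation. The SD of the difference is 18.21 x √2 = 25.75, and the noncentrality at N = 34 is 14/25.75 x √34 = 3.17. A cross-over t-test with N - 2 degrees of freedom, N even, then gives:

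| Reading of alpha | N for 85% power | Power at 34 |
|---|---|---|
| 0.025 one-sided (same critical value as 0.05 two-sided) | 34 | 86.7% |
| 0.025 two-sided | 40 | 78.9% |

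So 34 is reproduced in this model on the first row. If 18.21 is instead the SD of the paired difference, N is 18 (one-sided) or 22 (two-sided), and neither matches. The comparison below starts from the plan's stated 85%.

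**Both predictors real, two-sided 0.025.** The critical values are 2.241 at 0.025 and 1.960 at 0.05. The noncentrality is 2.241 + 1.036 = 3.278. Power at 0.05 is Φ(3.278 - 1.960) = 90.6%.

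For independent tests the results follow by hand:

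- Both, Bonferroni: 0.85² = 72.3%.
- Both, Holm: 2 x 0.85 x 0.906 - 0.85² = 81.8%.
- One given predictor, Holm: 0.85 + 0.85 x (0.906 - 0.85) = 89.8%.
- At least one, either procedure: 1 - 0.15² = 97.8%.

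With correlated tests (bivariate normal):

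| rho | Per predictor, Bonferroni → Holm | Both, Bonferroni → Holm | At least one (same for both) |
|---|---|---|---|
| 0 | 85.0% → 89.8% | 72.3% → 81.8% | 97.8% |
| 0.5 | 85.0% → 88.9% | 75.8% → 83.6% | 94.2% |
| 0.8 | 85.0% → 88.2% | 79.1% → 85.5% | 90.9% |

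On a one-sided reading the gain is similar. Power for both rises from 72.3% to 82.8% at rho 0 and from 79.1% to 86.0% at rho 0.8.

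**One predictor real, the other null (two-sided, simulated).** Power for the real predictor goes from 85.0% to about 85.1-85.2%. The false-positive rate for the null predictor goes from 2.5% to 4.6% (rho 0), 4.4% (rho 0.5) or 4.0% (rho 0.8).

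**Both null (simulated).** The chance of any false positive is the same under the two procedures: 4.9% at rho 0 and 4.6% at rho 0.5. Under this null, each procedure makes a false positive exactly when the smaller p-value is at or below 0.025.

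**The case against.** The strongest reply is that the documents do not commit the analysis to plain Bonferroni. It stands only in the sample-size text, and sizing each test at 0.025 is equally compatible with a Holm analysis. That is correct. The documented gap is an unnamed procedure, and the efficiency loss follows only if the 0.025 is applied as written. Since it is the only rule given, that is the natural reading.

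Three stronger readings are tempting, and the documents support none of them.

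- A reader might infer that Bonferroni is pure loss because error control is unchanged. That is exact only when both predictors are null. With one real and one null, Bonferroni holds the null one at 2.5%, against about 4-4.6% under Holm. Both are within 5%, but Bonferroni does buy something. It also gives simple simultaneous 97.5% confidence intervals, which Holm does not.
- A reader might infer that the trial's main hypothesis loses power. It does not. The hypothesis is met by MPT or HPT, and the chance of showing at least one is identical under the two procedures.
- A reader might take the gain as unconditional. It requires both effects to be real, and the figures take each at 85% power. The plan gives one effect size for two predictors and does not show that both attain it.

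The base is also uncertain. If 0.025 is two-sided, power at 34 is about 79% in the cross-over model above. Absolute powers would then be lower under both procedures, but the direction of the comparison stays the same. From a base of 82.3% (normal approximation), Holm gives 87.6% per predictor at rho 0 and 86.6% at rho 0.5.

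**Conclusion.** The point holds as a worthwhile, low-cost improvement. Bonferroni at 0.025 is valid and nothing in the error control is broken. For two aims listed separately, Holm is at least as powerful within the same implied 5% limit under any dependence. If both predictors are real with 85% power each, it adds about 3 to 5 percentage points per predictor and about 6 to 10 points for confirming both. If only one is real it adds almost nothing, and the null predictor's false-positive rate moves closer to 5%.

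These sizes rest on the stated 85% power, on two-sided tests (the one-sided results are similar) and on an assumed correlation of 0 to 0.8. That Holm rejects whatever Bonferroni rejects, and keeps to the 5% limit, rests on none of these. The silence of section 2.5.7 on alpha, sidedness and procedure is a plain fact of the text and should be corrected whichever procedure is chosen.

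**What to change.** In section 2.5.7, before unblinding:

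1. State that the MPT and HPT slope-difference tests are controlled at a familywise 0.05 by Holm: the smaller p-value is compared with 0.025 and, if significant, the larger with 0.05.
2. State whether the tests are one-sided or two-sided, and make this agree with the sample-size calculation. The same edit should say whether 18.21 is a per-period SD or the SD of the paired difference, because the figure of 34 depends on both.
3. Report 97.5% confidence intervals for both slope differences. Add that, with two-sided tests, a predictor significant only at the second Holm step (p between 0.025 and 0.05) will have a 97.5% interval that includes zero.

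Keep the sample-size calculation at the 0.025 level, since the first Holm step is made there. The change to Holm costs a sentence in the analysis section and needs no extra patients or data. If the sponsor prefers Bonferroni for its intervals or its tighter control of a single null predictor, that is defensible, but section 2.5.7 should say so.

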2.5.9 Clinical Procedures and Laboratory Tests

Due to the risk of decreased clearance of lidocaine in participants with moderate to severe renal or hepatic insufficiency, active surveillance to prevent drug accumulation will be performed. Plasma creatinine and liver transaminases will be determined before the study procedure in subjects with history of or suspected renal or hepatic disorders. If renal insufficiency ($SCr >1.5$ mg/dL or creatinine clearance < 50 mL/min/1.73m² [by Cockcroft-Gault formula]) or hepatic insufficiency (ALT or AST more the twice the

upper normal limit, or serum albumin below 3.5 g/dL) is present, the subject will be withdrawn from the study.

Due to increased risk of cardiac arrhythmias with lidocaine, patients with history of arrhythmias will be excluded. To increase safety, all patients with history of cardiac disease will be examined by 12-lead ECG to exclude active arrhythmias.

The patients will continue their chronic medications; including chronic pain medications, provided the dose have been stable for at least 3 weeks. Any PRN analgesics will not be allowed for 24 hours prior to each of the study visits.

3.0 Management of Intercurrent Events

3.1 Adverse Experiences

The investigator will closely monitor subjects for evidence of systemic lidocaine adverse events. All adverse events will be reported and followed until satisfactory resolution. The description of the adverse experience will include the time of onset, duration, severity, etiology, relationship to the study drug (none, unlikely, possible, probable, highly probable), and any treatment required.

In case of mild tachy- or brady- arrhythmias, or oxygen desaturation, the infusion will be paused, and attempted to resume 5 minutes after resolution of the adverse effect. The resumed infusion rate may be reduced from 7.5mg/kg/h to 5mg/kg/h, at the discretion of the PI. In any case of moderate to severe tachy- or brady- arrhythmias, or oxygen desaturation, the infusion will be stopped, and patient withdrawn from the study. In any case of serious side effects, the study team will follow the American Society of Regional Anesthesi (ASRA) guidelines on systemic local anesthetic toxicity [28]. Resuscitation kit and Intralipid[®] infusion for possible local anesthetic systemic adverse effect management will be readily available.

3.2 Premature Discontinuation

If a subject withdraws from the study, the subject will be replaced in order to provide the required number of evaluable subjects. Subjects will be withdrawn if the investigator decides that discontinuation is in the best interest of the subject, or the subject requests withdrawal from the study.

3.3 Potential Risks

3.3.1 Potential risks from lidocaine

Local anesthetic systemic effects associated with high plasma concentration may cause cardiac arrhythmias or neurologic adverse effects such as dizziness or drowsiness. Muscular twitching, convulsions and unconsciousness have been reported with inadvertent high dose intravascular boluses. Patients may experience blurred vision, dry mouth or perioral numbness. However, we have used this exact protocol in studies previously, and no patient had to discontinue treatment because of adverse effects. Moreover, in this study we will base the dosing on ideal body weight instead of actual weight, which will result in lower lidocaine doses, and eventually reduced risk of adverse effects. Intravenous lidocaine is FDA-approved for the treatment of cardiac arrhythmias, used by infusion in concentrations between 4-8mg/mL. In this study, the final concentration of infused lidocaine is expected to be between 4-6mg/mL, based on subjects' IBW, which falls within the approved concentration and dosage. We have limited the allowed dose to 500mg lidocaine to prevent serious systemic adverse effects. The serious systemic adverse effects of local anesthetics have typically occurred from inadvertent intravascular bolus injections of solution intended for regional anesthesia. Adverse effects such as muscle twitching, unconsciousness and convulsions have been usually reported following plasma lidocaine concentrations of >12 mcg/mL. In this study, lidocaine is administered by slow IV infusion, and the resulting peak plasma concentrations are not expected to exceed 3-4mcg/mL, per previous studies. However, in case of

any serious side effects, the study team will follow ASRA guidelines on systemic local anesthetic toxicity [28]. No psychological risks to subjects are envisioned.

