Patients' demographic data will be recorded; height and weight will be measured. The subject will be asked to complete the Brief Pain Inventory (BPI) AND Hospital Anxiety and Depression Scale (HADS). Subjects who drop out of the study prior to completing the study will be replaced by using the next available patient number.

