At each of the intervention visits, an intravenous catheter will be inserted in the arm for drug administration, and in the opposite arm for obtaining blood samples to evaluate the plasma concentrations of lidocaine. The dose of lidocaine will be 5mg/kg ideal body weight (IBW), calculated by B. J. Devine Formula:

$$IBW = 50.0 + 2.3 \text{ kg per inch over 5 feet} \quad (\text{man})$$

$$IBW = 45.5 + 2.3 \text{ kg per inch over 5 feet} \quad (\text{woman})$$

Lidocaine will be infused during 40 minutes. The unblinded investigator will prepare 100mL normal saline infusion bags either with lidocaine or the same volume of normal saline (placebo). For lidocaine infusion, saline will be first drawn from the infusion bag in a volume equal to lidocaine volume to be added to the infusion, to keep the same total volume of the infusion bag. The total lidocaine dose will be limited to 500mg for safety reasons. The subjects will have continuous 3-lead ECG monitoring for 90 minutes.

Prior to infusion, we will assess:

1. Spontaneous pain intensity on 0-10 NRS.
2. NPSI pain descriptors burning, squeezing, pins and needles, tingling, stabbing, electrical shocks) on 0-10 scale
3. Evoked response (0-10 NRS) to cold (20°C, Rolltemp, Somedic), warm (40°C, Rolltemp, Somedic), brush (Senselab brush-05, Somedic) and pinprick (256mN metal probe, MRC Systems) stimuli applied to a dorsal foot and a non-painful control site (ipsilateral shoulder).

Tabular description of the study assessments is available in Table 1.

Table 1. Data assessment schedule

Required Assessments	Baseline visit	Treatment Visit 1	Washout			Treatment visit 2	Week 1b	Week 2b	Week 3b	End of Study communication
			Week 1a	Week 2a	Week 3a					
Informed consent	✓									
Inclusion/exclusion criteria	✓									
Randomization	✓									
Demographic data collection	✓									
BPI questionnaire	✓									
HADS questionnaire	✓									
Sensory Mapping	✓									
Assessment of sensitivity to cold, warm, brus and pinprick		✓				✓				
NoL measurement		✓				✓				
NPSI questionnaire		✓				✓				
QST		✓				✓				
CPM		✓				✓				
Blood sampling for PK		✓				✓				
Pain intensity 0-10 NRS		✓	daily	daily	daily	✓	daily	daily	daily	✓
Adverse Event assessment		✓				✓				✓
Blinding questionnaire										✓

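### Dosing on ideal body weight raises, rather than lowers, the lidocaine dose in a patient lighter than ideal weight, and nothing in the dosing rule prevents this

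*Combined protocol and SAP*

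**What the plan says.** Section 2.5.3 (Study Period) sets the rule: "The dose of lidocaine will be 5mg/kg ideal body weight (IBW), calculated by B. J. Devine Formula". The formula starts from 50.0 kg for a man or 45.5 kg for a woman and adds 2.3 kg for each inch above 5 feet. The only limit on the result is an absolute one: "The total lidocaine dose will be limited to 500mg for safety reasons". Actual weight does not enter the rule, although section 2.5.2 records that "height and weight will be measured".

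Section 3.3.1 (Potential risks from lidocaine) then gives the choice of IBW as a safety feature: "we will base the dosing on ideal body weight instead of actual weight, which will result in lower lidocaine doses, and eventually reduced risk". The same section states that "peak plasma concentrations are not expected to exceed 3-4mcg/mL" and places the more serious neurological effects above 12 mcg/mL.

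The eligibility lists in sections 2.4.1 and 2.4.2 and the clinical and laboratory checks in section 2.5.9 contain no minimum weight or BMI.

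**The concern.** The statement in section 3.3.1 has no qualifier, but its truth depends on the patient. Replacing actual weight by IBW lowers the dose when actual weight is above IBW and raises it when actual weight is below. The plan neither excludes the second group nor handles it in the dosing rule.

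What is at stake is the safety rationale for lean patients. They would receive more than 5 mg per kg of actual weight under a rule presented as dose-reducing. Section 2.2 reports that at 5 mg/kg the infusion was briefly paused in 6 of 14 earlier patients for transient dizziness or blurred vision, so tolerability at that dose already has some limits. The contrast drawn in section 3.3.1 implies that the earlier dosing used actual weight. If so, a lean patient in this trial would exceed the per-kilogram dose on which the cited safety experience rests.

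**Working it through.** **Inputs from the documents.** Dose 5 mg per kg IBW, the Devine formula, the 500 mg cap and the 40-minute infusion (section 2.5.3); infusion rate 7.5 mg/kg/h (section 3.1); expected peak of at most 3-4 mcg/mL and serious effects above 12 mcg/mL (section 3.3.1).

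**Inputs assumed.** Heights and BMIs are illustrative, because the documents give no weight distribution.

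**Step 1: reproduce the plan's own rate.** 5 mg/kg ÷ (40/60 h) = 7.5 mg/kg/h, which matches section 3.1. The dose and duration are consistent; the question is only which weight is used.

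**Step 2: where the two dosing bases cross.** Protocol dose = 5 × IBW. Actual-weight dose = 5 × W, where W = BMI × height(m)². They are equal when BMI = IBW ÷ height(m)².

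- Men: 62 in, 22.0; 69 in, 70.7 ÷ 1.7526² = 23.0; 72 in, 23.2.
- Women: 60 in, 19.6; 64 in, 54.7 ÷ 1.6256² = 20.7; 68 in, 21.4.

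Below these values the IBW rule gives the larger dose. Above them it gives the smaller one, as section 3.3.1 says.

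**Step 3: size of the excess.**

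Man, 69 in: IBW = 50.0 + 2.3 × 9 = 70.7 kg; dose = 5 × 70.7 = 353.5 mg.
Woman, 64 in: IBW = 45.5 + 2.3 × 4 = 54.7 kg; dose = 5 × 54.7 = 273.5 mg.

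| Patient | BMI | Actual weight (kg) | Dose on actual weight (mg) | Dose under the rule (mg) | Excess (mg) | mg per kg actual | Change |
|---|---|---|---|---|---|---|---|
| Man, 69 in | 20 | 61.4 | 307 | 353.5 | 46 | 5.75 | +15% |
| Man, 69 in | 18.5 | 56.8 | 284 | 353.5 | 69 | 6.2 | +24% |
| Woman, 64 in | 20 | 52.9 | 264 | 273.5 | 9 | 5.2 | +3.5% |
| Woman, 64 in | 18.5 | 48.9 | 244 | 273.5 | 29 | 5.6 | +12% |

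Over heights of 60-76 in, the change at BMI 18.5 is +16% to +26% in men and +6% to +19% in women. At BMI 20 it is +8% to +17% in men and -2% to +10% in women.

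**Step 4: does the cap help?** The cap binds when 5 × IBW = 500 mg, that is, at IBW = 100 kg. For a man this needs 60 + (100 - 50.0) ÷ 2.3 = 81.7 in; for a woman, 60 + (100 - 45.5) ÷ 2.3 = 83.7 in. At ordinary heights it does nothing.

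**Step 5: what it could mean for plasma levels.** Assume that the stated 3-4 mcg/mL peak applies at 5 mg/kg actual weight and scales with dose. The largest example in the table, with ratio 353.5 ÷ 284.1 = 1.244, then gives 3 × 1.244 = 3.7 to 4 × 1.244 = 5.0 mcg/mL. That can pass the 4 mcg/mL the plan does not expect to exceed, but stays well below 12 mcg/mL.

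**The case against.** The best reply is that section 3.3.1 compares this study with earlier ones and is not a promise about each patient. Read that way it may well be true on average, and the dosing rule itself is unambiguous and can be carried out as written. No affected patient has been shown: every figure above depends on a chosen BMI, and some short women at BMI 20 would receive slightly less under the IBW rule. The largest tabulated dose, 353.5 mg, is far below the 500 mg ceiling. All patients have ECG and oximetry monitoring, can pause or stop the infusion, and are covered by the rate-reduction and stopping rules in sections 3.1 and 3.4. On this view, adding a phrase such as *in patients above their IBW* to section 3.3.1 would be enough. A lesser-of rule would be a design preference, with no evidence in the documents that actual weight is the better basis for lean patients.

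Most of this stands as a limit on importance. The group-level reading is possible, the affected number is unknown, and the projected exposure is not alarming. The plasma projection also rests on an attribution that the documents do not establish. What does not stand is the conclusion that rewording is enough. It would make the sentence accurate but leave lean patients on a higher per-kilogram dose, with no reason given for wanting that. Monitoring responds to adverse effects after they appear; the purpose stated in section 3.3.1 is to reduce the risk through the dose.

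**Conclusion.** The concern holds and is minor. By the protocol's own formula, IBW dosing increases the dose for any eligible patient below IBW (apart from the trivial case of such a patient weighing 100 kg or more, who is capped at 500 mg either way). For men of 62-72 in this begins below a BMI of about 22.0-23.2, which includes ordinary lean builds; for women of 60-68 in, below about 19.6-21.4. How many of the 35 evaluable patients would be affected cannot be judged from the documents. The direction of the error is certain, while its size depends on the assumed heights and BMIs. The primary analysis, power and sample size are not touched.

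**What to change.** Change the dosing basis in section 2.5.3 to something like: *Lidocaine is dosed at 5 mg per kg of whichever is lower, Devine IBW or the actual body weight measured at enrolment, up to a maximum of 500 mg.* Section 3.3.1 can then state that no patient receives a higher dose than under actual-weight dosing.

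The cost is one clause. Weight is already collected, so no procedure is added, and patients at or above IBW are dosed exactly as now. Blinding is unaffected, because the lidocaine volume replaces an equal volume of saline in the bag. The downside is a smaller absolute dose in lean patients, still 5 mg per kg of actual weight: at BMI 18.5, 284 mg instead of 354 mg for the 69 in man, and 244 mg instead of 274 mg for the 64 in woman. If the sponsor prefers to keep plain IBW dosing, section 3.3.1 should at least limit its claim to patients above IBW and say why a higher per-kilogram dose is acceptable in the others.
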